4.2. Patient Exclusion Criteria

Patients will not be randomized/enrolled in this study if they meet any of the following criteria:

- a. The patient has used systemic steroids for any medical reason (including treatment of the current CH cycle) within ≤ 7 days prior to screening.
- b. The patient reports using butalbital on more than 7 days during the 4 weeks prior to screening or using butalbital on more than 3 days during the screening/run-in period.
- c. The patient reports using opioids on more than 15 days during the 4 weeks prior to screening or using opioids on more than 4 days during the screening/run-in period.
- d. The patient has used an intervention/device (eg, scheduled nerve blocks) for headache during the 4 weeks prior to screening.
- e. The patient has clinically significant hematological, renal, endocrine, immunologic, pulmonary, gastrointestinal, genitourinary, cardiovascular, neurologic, hepatic, or ocular disease at the discretion of the investigator.
- f. The patient has evidence or medical history of clinically significant psychiatric issues determined at the discretion of the investigator.
- g. The patient has a history of any suicide attempt in the past or current active suicidal ideation, as measured by the eC-SSRS.
- h. The patient has a history of clinically significant cardiovascular disease or vascular ischemia (such as myocardial, neurological [eg, cerebral ischemia], peripheral extremity

ischemia, or other ischemic event) or thromboembolic events (arterial or venous thrombotic or embolic events), such as cerebrovascular accident (including transient ischemic attacks), deep vein thrombosis, or pulmonary embolism.

- i. The patient has a past or current history of cancer or malignant tumor in the past 5 years, except for appropriately treated non-melanoma skin carcinoma.
- j. The patient is pregnant or lactating.
- k. The patient has a history of hypersensitivity reactions to injected proteins, including monoclonal antibodies.
- l. The patient has participated in a clinical study of a new chemical entity or a prescription medicine within 2 months or 5 half-lives before administration of the first dose of the IMP, whichever is longer.
- m. The patient has participated in a clinical study of a monoclonal antibody within 3 months or 5 half-lives before administration of the first dose of the IMP, whichever is longer, unless it is known that the patient received placebo during the study.
- n. The patient has a history of prior exposure to a monoclonal antibody targeting the CGRP pathway (AMG 334, ALD304, LY2951742, or fremanezumab). If patient has participated in a clinical study with any of these monoclonal antibodies, it has to be confirmed that the patient received placebo in order to be eligible for this study.
- o. The patient has any finding in the baseline 12-lead ECG considered clinically significant in the judgment of the investigator.
- p. The patient has any finding that, in the judgment of the investigator, is a clinically significant abnormality, including serum chemistry, hematology, coagulation, and urinalysis test values (abnormal tests may be repeated for confirmation).
- q. The patient has hepatic enzymes (ALT and AST) $>1.5 \times$ the upper limit of normal (ULN) range after confirmation in a repeat test, or the patient has suspected hepatocellular damage that fulfills criteria for Hy's law at screening.
- r. The patient has serum creatinine $>1.5 \times$ the ULN or evidence of clinically significant renal disease in the judgement of the investigator.
- s. The patient cannot participate or successfully complete the study, in the opinion of their healthcare provider or the investigator, for any of the following reasons:
 - mentally or legally incapacitated or unable to give consent for any reason
 - in custody due to an administrative or a legal decision, under tutelage, or being admitted to a sanitarium or social institution
 - unable to be contacted in case of emergency
 - has any other condition, which, in the opinion of the investigator, makes the patient inappropriate for inclusion in the study
- t. The patient is an employee of the sponsor/participating study center who is directly involved in the study or is the relative of such an employee.

- u. The patient has an active implant for neurostimulation used in the treatment of CH.
- v. The patient is a member of a vulnerable population (eg, people kept in detention).
- w. The patient has a history of alcohol and/or drug abuse that in the investigator’s opinion could interfere with the study evaluations or the patient’s safety.

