4.1. Patient Inclusion Criteria

Patients may be randomized/enrolled in this study only if they meet all of the following criteria:

- a. Patients are capable of giving signed informed consent as described in [Appendix D](#) which includes compliance with the requirements and restrictions listed in the informed consent form (ICF) and in this protocol.
- b. The patient is a man or woman 18 to 70 years of age, inclusive.
- c. The patient has a history of ECH according to ICHD-3 beta criteria ([Headache Classification Committee of the IHS 2013](#)) for ≥ 12 months prior to screening including the following:
 - Attacks of severe, strictly unilateral pain which is orbital, supraorbital, temporal or in any combination of these sites, lasting 15 to 180 minutes and occurring from once daily every other day to 8 times a day for more than half of the time when the disorder is active.
 - The pain is associated with at least 1 of the following symptoms or signs: ipsilateral conjunctival injection, lacrimation, nasal congestion, rhinorrhea, forehead and facial sweating, miosis and/or ptosis and/or eyelid edema, and/or sense of restlessness or agitation.
 - CH attacks occurring in periods lasting from 7 days to 1 year, separated by pain-free periods lasting at least 1 month.
- d. CH attacks of a new cluster cycle have started within ≤ 2 weeks (14 days, inclusive) prior to screening and, based on the patient's previous medical history, it is expected that the patient's CH attacks will continue for ≥ 6 weeks after the screening visit.
- e. The patient has a total body weight of ≥ 45 kg
- f. The patient is not using or using ≤ 2 concomitant medications that are commonly prescribed as preventive treatments for CH ([Appendix H](#)), regardless of the indication for which the medication was prescribed. Patients must be on a stable dose and regimen for at least 2 weeks prior to screening and throughout the study.
- g. If a patient is receiving Botox, it should be in a stable dose regimen, considered as having ≥ 2 cycles of Botox prior to screening. The patient should not receive Botox during the run-in period up to the evaluation period (4 weeks) where the primary endpoint is evaluated.
- h. The patient has demonstrated compliance with the electronic headache diary during the run-in period by entry of headache data on 85% of days during the run-in period.

- i. The patient has at least 7 CH attacks during the run-in period.

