4.3. Withdrawal Criteria and Procedures

Each patient is free to withdraw from the IMP and/or study at any time, without prejudice to their continued care. Patients must be withdrawn from the IMP and/or study if any of the following events occur:

1. Patient withdraws consent or requests discontinuation from the IMP and/or study for any reason.
2. Patient develops an illness that would interfere with his/her continued participation.
3. Patient is noncompliant with the study procedures and assessments or administration of IMPs in the opinion of the investigator.
4. Patient takes prohibited concomitant medications as defined.
5. A female patient has a confirmation of pregnancy during the study from a positive pregnancy test.
6. The sponsor requests withdrawal of the patient.
7. Patient experiences an adverse event or other medical condition which indicates to the investigator that continued participation is not in the best interest of the patient.
8. The investigator and/or sponsor may withdraw an individual patient from the study at any time for any reason (eg, lack of efficacy, protocol deviation as defined in Section 10, noncompliance, or adverse event). In addition, patients with positive eC-SSRS findings or abnormal hepatic laboratory values (eg, ALT, AST, ALP, GGT, bilirubin [total, direct, or indirect], or INR) may meet criteria for discontinuation from the IMP as summarized in [Appendix J](#).

In the event that a patient was incorrectly randomized and has already started taking the study drug, a risk/benefit evaluation should take place between the investigator and sponsor and a strong clinical justification must be provided if the patient is not withdrawn from study drug.

Patients should be treated with standard of care after withdrawal from or termination of the study as appropriate.

Investigators should attempt to obtain information on patients in the case of withdrawal or discontinuation. Results of any evaluations and observations, together with a narrative describing the reason(s) for withdrawal, must be recorded in the source documents. The case report form (CRF) must document the primary reason for withdrawal or discontinuation.

See [Appendix F](#) for information regarding how the study will define and address lost to follow-up patients to help limit the amount and impact of missing data.

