7.10. Concomitant Therapy or Medication

Concomitant therapy or medication use will be monitored throughout the study. Details of prohibited medications are found in Section 5.6.

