APPENDIX H. PREVENTIVE CLUSTER HEADACHE MEDICATIONS AND DISALLOWED MEDICATIONS

1. Medications Commonly Prescribed for Cluster Headache

The following medications will be considered as being used for the prevention of cluster headaches, regardless of the initial indication.

- verapamil
- lithium
- methysergide
- valproate
- topiramate

Patients are allowed to take up to 2 of these medications provided that they are on a stable dose and regimen for at least 2 weeks prior to screening and throughout the study.

If a patient is receiving Botox, it should be in a stable dose regimen, considered as having ≥ 2 cycles of Botox prior to screening. The patient should not receive Botox during the run-in period up to the evaluation period (4 weeks) where the primary endpoint is evaluated.

2. Concomitant Medications Allowed and Disallowed

Steroids:

Screening/run-in period and throughout the study: Systemic steroids are not allowed to be used in the treatment of cluster cycles during the screening/run-in period and for the duration of the study.

The only allowed steroids are intra-articular injection or ocular, ear drops, intranasal, inhaled, and creams for topical use.

Screening/run-in period: Disallowed if patient has used systemic steroids for any medical reason (including treatment of the current CH cycle) within ≤ 7 days of screening.

Butalbital:

Screening/run-in period: Disallowed if used more than 3 days during the screening/run-in period. Patients can use butalbital as needed (PRN) after randomization into the study.

Opioids:

Screening/run-in period: Disallowed if used more than 4 days during the screening/run-in period. Patients can use opioids PRN after randomization into the study.

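### Exclusion d stops at screening, so an anaesthetic-only nerve block or non-implanted device used in the run-in passes eligibility, and the protocol does not state the status of such use after randomization

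*Protocol*

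**What the plan says.** Protocol Section 4.2, exclusion d, reads: "The patient has used an intervention/device (eg, scheduled nerve blocks) for headache during the 4 weeks prior to screening". It has no clause for the run-in or the treatment period.

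Other eligibility items go further. Exclusion b adds a second limit, "or using butalbital on more than 3 days during the screening/run-in period", and exclusion c adds "or using opioids on more than 4 days during the screening/run-in period". In Section 4.1, inclusion g says of Botox: "The patient should not receive Botox during the run-in period up to the evaluation period (4 weeks) where the primary endpoint is evaluated". Appendix H bars systemic steroids during the run-in and for the rest of the study.

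For treatment after randomization, Section 4.3, item 4, requires withdrawal when "Patient takes prohibited concomitant medications as defined". Section 7.10 says where the definition is: "Details of prohibited medications are found in Section 5.6". Section 5.6 prohibits nothing by name. It requires medications, treatments and procedures to be recorded up to the end of the study, and preventive and daily medications to be stable. Appendix H deals with five preventive drugs, Botox, steroids, butalbital and opioids. On steroids it says: "The only allowed steroids are intra-articular injection or ocular, ear drops, intranasal, inhaled, and creams for topical use". It has no entry for nerve blocks or devices.

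**The concern.** By asking for 4 clear weeks, the sponsor treats headache interventions and devices as able to alter attack counts. Yet the days that supply the baseline, and the 4 weeks that supply the primary endpoint, are not covered by that rule. A block given the day before screening excludes the patient; the same block a few days later does not.

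Two things are at stake. The first is the run-in baseline, from which every change score is measured. The second is the week 0 to 4 count. If treatment of this kind is used after dosing more often by patients who are not improving, it would narrow the observed difference. With no stated status, sites may also handle such patients differently.

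**Working it through.** **Text check.**

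| Item | Before screening | Run-in | After randomization |
|---|---|---|---|
| Butalbital (exclusion b, Appendix H) | limit | limit | allowed as needed |
| Opioids (exclusion c, Appendix H) | limit | limit | allowed as needed |
| Botox (inclusion g, Appendix H) | stable regimen | barred | barred through the 4-week primary window |
| Systemic steroids (exclusion a, Appendix H) | 7-day limit | barred | barred |
| Active neurostimulation implant for cluster headache (exclusion u) | excluded | excluded | not separately stated |
| Other interventions/devices (exclusion d) | 4-week limit | nothing stated | nothing stated |

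Eligibility is reviewed again at visit 2 (Protocol Table 2 and Appendix B). That review cannot catch run-in use under exclusion d, because its window is tied to screening. A block containing a steroid conflicts with the Appendix H list of allowed steroid routes, and an active implant falls under exclusion u. What remains is the anaesthetic-only block and the non-implanted device.

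The per-protocol set in SAP Section 3.4 removes non-completers, eligibility violations and dosing violations. A patient with such use breaks none of these and stays in.

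**Effect of run-in use.** In a 7-day run-in, a block on day 5 leaves 4 of 7 baseline days (57%) before the block, and one on day 7 leaves 6 of 7 (86%). All of weeks 0 to 4 then follow it. Allocation happens afterwards, so the expected share of such patients is the same in each arm.

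**Effect of use after dosing.** The planning inputs are in Protocol Section 9.1: difference 1, SD 2, 86 per arm, two-sided alpha 0.05. The plan's own figure reproduces: a two-sample t-test gives 90.3% power (90.6% by the normal approximation) against a stated minimum of 90%.

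The documents give no rate of use and no effect size. The following are assumptions: 5% of placebo and 2% of active patients, or 10% and 4%, with each use lowering that patient's 4-week average by 3 or 5 attacks per week.

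Dilution = (placebo rate − active rate) × effect; power is then taken at (1 − dilution).

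| Rates | Effect | Dilution | Remaining difference | Power, 86 per arm | Power, 100 per arm |
|---|---|---|---|---|---|
| 5% v 2% | 3 | 0.03 × 3 = 0.09 | 0.91 | 84.3% | 89.3% |
| 5% v 2% | 5 | 0.03 × 5 = 0.15 | 0.85 | 79.1% | 84.9% |
| 10% v 4% | 3 | 0.06 × 3 = 0.18 | 0.82 | 76.2% | 82.3% |
| 10% v 4% | 5 | 0.06 × 5 = 0.30 | 0.70 | 62.6% | 69.3% |

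The last column is shown because the primary analysis uses the full analysis set, which needs only 10 diary days in the first 4 weeks (SAP Section 3.3), so the analysed number could approach 100 per arm. The table assumes the whole 4-week average is lowered. If use came at mid-window, the 0.15 case would halve to 0.075, with 85.4% power at 86 per arm.

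**The case against.** The strongest reply is that the protocol loosens its restrictions after randomization on purpose. Acute medication is allowed for any attack, and Appendix H lets patients use butalbital and opioids as needed once randomized. Exclusions b and c therefore support a run-in clause only. That stands, and it is why no on-study rule is proposed here. It does not settle the matter, because butalbital and opioids are expressly permitted while interventions and devices are not mentioned.

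Second, the gap is narrow: exclusion u and the steroid routes in Appendix H already remove part of it. That also stands. A reader might infer from exclusion d that every block or device is unregulated after screening, or that Appendix H covers only steroids, butalbital and opioids. Neither is right.

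Third, a reader might infer that run-in use biases the comparison between arms. It precedes randomization, so the documents do not support that.

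Fourth, a reader might take the power figures as a forecast. They rest on assumed rates and effects, relate only to use after dosing, and would not be improved by changing exclusion d. A bias towards zero would not create a false positive result.

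Fifth, investigators and the sponsor may withdraw patients at their discretion (Section 4.3), and Section 5.6 could be read as barring unlisted preventives by implication. Discretion does not define a treatment as prohibited, and Section 5.6 concerns medications, so it does not reach devices.

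Finally, SAP Section 3.5, most of the multiple-imputation text and parts of the exploratory analyses are blacked out. It cannot be said that no handling rule exists, only that none is visible.

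**Conclusion.** The gap in the text is real. Exclusion d leaves the baseline period open to an anaesthetic-only block or a non-implanted device, and the sections on concomitant treatment do not state the status of such use after randomization.

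Run-in use costs precision and room for a drug effect; it does not bias the arms against each other. For use after dosing, dilution is plausible only if use is commoner in patients who are not improving, and the documents do not allow its size to be estimated. The range of 0.09 to 0.30 attacks per week, or about 84% to 63% power at 86 per arm and SD 2, is illustrative. The planned sample size sits almost exactly at 90% power, so there is little reserve at 86 per arm. This is a cheap improvement to the plan, not a flaw that undermines the primary result.

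**What to change.** 1. Extend the window of exclusion d to the screening/run-in period, in line with exclusions b and c, and check it at visit 2.
2. Reconcile Sections 4.3 (item 4), 5.6 and 7.10 and Appendix H so that the status of interventions and devices after randomization is stated. The rule itself is the sponsor's to set. The reference in Section 7.10 should lead to the place where the rule is found.
3. Add a supplementary analysis of the primary endpoint that sets diary days after a first on-study intervention or device use to missing, and state how those days are then handled. Label it supplementary, because it targets a different estimand: the outcome had such treatment not been used. Section 5.6 already has treatments and procedures recorded. It spells out start and end dates for medications, so confirm that the entries for procedures and devices are dated too.

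The cost is a few more screen failures and one additional table. If those entries are dated, no new data are collected.

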4.3. Withdrawal Criteria and Procedures

Each patient is free to withdraw from the IMP and/or study at any time, without prejudice to their continued care. Patients must be withdrawn from the IMP and/or study if any of the following events occur:

1. Patient withdraws consent or requests discontinuation from the IMP and/or study for any reason.
2. Patient develops an illness that would interfere with his/her continued participation.
3. Patient is noncompliant with the study procedures and assessments or administration of IMPs in the opinion of the investigator.
4. Patient takes prohibited concomitant medications as defined.
5. A female patient has a confirmation of pregnancy during the study from a positive pregnancy test.
6. The sponsor requests withdrawal of the patient.
7. Patient experiences an adverse event or other medical condition which indicates to the investigator that continued participation is not in the best interest of the patient.
8. The investigator and/or sponsor may withdraw an individual patient from the study at any time for any reason (eg, lack of efficacy, protocol deviation as defined in Section 10, noncompliance, or adverse event). In addition, patients with positive eC-SSRS findings or abnormal hepatic laboratory values (eg, ALT, AST, ALP, GGT, bilirubin [total, direct, or indirect], or INR) may meet criteria for discontinuation from the IMP as summarized in [Appendix J](#).

In the event that a patient was incorrectly randomized and has already started taking the study drug, a risk/benefit evaluation should take place between the investigator and sponsor and a strong clinical justification must be provided if the patient is not withdrawn from study drug.

Patients should be treated with standard of care after withdrawal from or termination of the study as appropriate.

Investigators should attempt to obtain information on patients in the case of withdrawal or discontinuation. Results of any evaluations and observations, together with a narrative describing the reason(s) for withdrawal, must be recorded in the source documents. The case report form (CRF) must document the primary reason for withdrawal or discontinuation.

See [Appendix F](#) for information regarding how the study will define and address lost to follow-up patients to help limit the amount and impact of missing data.

If a patient is withdrawn from the study for multiple reasons that include also adverse events, the termination page of the CRF should indicate that the withdrawal was related to an adverse event.

An exception to this requirement will be the occurrence of an adverse event that in the opinion of the investigator is not severe enough to warrant discontinuation but that requires the use of a prohibited medication, thereby requiring discontinuation of the patient. In such a case, the reason for discontinuation would be “need to take a prohibited medication” and not the adverse event.

Should a patient decide to withdraw after administration of the IMP or should the investigator decide to withdraw the patient, all efforts will be made to complete and report all observations up to the time of withdrawal. A complete final evaluation at the time of the patient’s withdrawal should be made and an explanation given as to why the patient is withdrawing or being withdrawn from the study.

The reason for and date of withdrawal from the study must be recorded on the source documentation and transcribed to the CRF. If a patient withdraws consent, every attempt will be made to determine the reason.

All protocol-specified procedures/assessments should be performed at the early withdrawal visit (see [Appendix B](#)). Patients who withdraw from the study will not be replaced. Patients who discontinue early for any reason will be offered the opportunity to enter in the long-term safety study (Study TV48125-CNS-30058) for the purpose of evaluation of ADAs and safety (adverse events and concomitant medications) approximately 7.5 months after administration of the last dose of IMP in this study. These patients will not receive any doses of fremanezumab after completing participation in the current study and should be treated with standard of care as appropriate.

A patient should only be designated as lost to follow up if the site is unable to establish contact with the patient after 3 documented attempts via 2 different methods (phone, text, e-mail, certified letter, etc). In the case of patients lost to follow-up, attempts to contact the patient must be made and documented in the patient’s medical records and transcribed to the CRF.

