APPENDIX C. QUALITY CONTROL AND QUALITY ASSURANCE

Protocol Amendments and Protocol Deviations

Protocol Amendments

No changes from the final approved (signed) protocol will be initiated without the prior written approval or favorable opinion of a written amendment by the Independent Ethics Committee/Institutional Review Board (IEC/IRB) and national and local competent authorities, as applicable, except when necessary to address immediate safety concerns to the patients or when the change involves only nonsubstantial logistics or administration. The principal investigator at each investigational center, the coordinating investigator (if applicable), and the sponsor will sign the protocol amendment.

Protocol Deviations

Any deviation from the protocol that affects, to a significant degree, (a) the safety, physical, or mental integrity of the patients in the study and/or (b) the scientific value of the study will be considered an important protocol deviation. Important protocol deviations may include non-adherence on the part of the patient, the investigator, or the sponsor to protocol-specific inclusion and exclusion criteria, primary objective variable criteria, or GCP guidelines; noncompliance to IMP administration; use of prohibited medications. All protocol deviations will be reported to the responsible IEC/IRB, as required.

When an important protocol deviation is reported, the sponsor will determine whether to discontinue the patient from the study or permit the patient to continue in the study, with documented approval from the medical expert. The decision will be based on ensuring the safety of the patient and preserving the integrity of the study. A noncompliant patient may continue taking the study treatment only if this does not jeopardize the patient's safety. The sponsor will assess each protocol deviation and decide whether any of these noncompliances should be reported to the Regulatory Authority as a serious breach of GCP and the protocol.

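### SAP 3.4 drops Protocol 9.2.4's exclusion for important deviations, so a patient kept in the trial after taking prohibited steroids, and who completes it, stays in the per-protocol set

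*Protocol*

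**What the plan says.** **Withdrawal.** Protocol Section 4.3 opens its list with "Patients must be withdrawn from the IMP and/or study if any of the following events occur", and item 4 reads "Patient takes prohibited concomitant medications as defined". A later paragraph covers an adverse event that "requires the use of a prohibited medication, thereby requiring discontinuation of the patient".

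**Deviations.** Appendix C gives examples of what may be an important protocol deviation, among them "noncompliance to IMP administration; use of prohibited medications". Once one is reported, "the sponsor will determine whether to discontinue the patient from the study or permit the patient to continue in the study". It also lets a noncompliant patient go on receiving study treatment if that is safe.

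**What is prohibited.** Appendix H states "Systemic steroids are not allowed to be used in the treatment of cluster cycles", from screening to the end of the study, and permits only a short list of local, nasal or inhaled steroids. Letter of Clarification 04 (Protocol 16.3) gives the sponsor's reason: steroids can mask an improvement.

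**Per-protocol set.** Protocol 9.2.4 keeps only patients free of important deviations, with these settled before unblinding and database lock. SAP 3.4 keeps patients who completed the study with no eligibility breach and no dosing error or missed dose. The SAP repeats the primary and secondary analyses in this set. The SAP introduction gives the SAP precedence over the protocol, and SAP Section 16 lists no changes to the protocol's analyses.

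**The concern.** A per-protocol analysis shows whether the result holds among patients who followed the plan in the ways that matter for efficacy. For this endpoint, prohibited steroids are an obvious departure. Protocol 1.1.2 names short courses of corticosteroids among the treatments used for cluster headache, and the sponsor bars them because they could hide what the study drug did.

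The protocol's definition would take such a patient out once the deviation is judged important. The SAP's definition would not. The trial could therefore report a per-protocol result as support for the primary analysis while it contains the same steroid-treated patients. A reader who relied on Protocol 9.2.4, or on the statement that nothing was changed, would not know.

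**Working it through.** No figure in the plan is in dispute here, so the check is a comparison of texts followed by a rough size.

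**1. The two definitions, side by side**

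| Situation | Protocol 9.2.4 | SAP 3.4 (readable text) |
|---|---|---|
| Did not complete the study | Out only if an important deviation | Out |
| Eligibility breach | Out if judged important | Out |
| Dosing error or missed dose | Out if judged important | Out |
| Prohibited medication after randomization | Out if judged important | Not mentioned |

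**2. Is post-randomization steroid use caught by another clause of SAP 3.4?**

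- Exclusion criterion a concerns systemic steroids in the 7 days before screening. Later use does not breach it.
- It is not an error or omission in giving the study drug.
- Some other medication departures are caught. A changed preventive dose, or Botox in the first 4 weeks, can breach inclusion criterion f or g. The gap is therefore about steroids, not every medication.

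**3. What happens to a patient who takes systemic steroids**

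- Withdrawn from the study under 4.3: a non-completer, so out under SAP 3.4.
- Withdrawn from study drug only, before the week 8 dose: a dose is missed, so out on a natural reading of SAP 3.4.
- Kept on study drug under Appendix C and completes: meets every condition of SAP 3.4, so **in**. Under Protocol 9.2.4, out if the deviation is judged important.
- Takes steroids after the week 8 dose and completes: no dose is left to miss, so **in**. This bears on the secondary endpoints that use weeks 8 to 12.

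The SAP has precedence, so the last two patients stay in.

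**4. Rough size in the per-protocol set**

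From the documents: at least 7 attacks in a 7- to 10-day run-in, so a minimum entry rate of 7 × 7/10 = 4.9 to 7.0 per week; 86 planned completers per group; planned difference 1 attack per week.

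Assumed, because the documents do not say: steroids start on day 15 (14 of 28 days treated) and cut attacks by 50% to 100%.

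- Drop in that patient's 4-week average: 4.9 × 0.5 × 0.5 = 1.225 at the low end, and 7.0 × 1.0 × 0.5 = 3.5 at the high end.
- Shift in the group mean per patient: 1.225/86 = 0.014 to 3.5/86 = 0.041 attacks per week.
- With 3 more such patients in one group than in the other: 0.043 to 0.122. With 5 more: 0.071 to 0.203.

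The difference shrinks if the excess is on placebo and widens if it is on active drug. The per-protocol set cannot exceed the completers, so if the planned 86 holds, each patient's weight is at least 1/86. Entry rates above the minimum would raise the figures. Excluding a patient removes the distorted value but does not recover the value without steroids. These figures therefore size the distortion, not the exact change the fix would make.

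**The case against.** **Inclusion criteria a and n.** They refer to compliance with protocol requirements and restrictions, so a breach of Appendix H might count as an eligibility violation that SAP 3.4 already covers. But they concern capacity to consent and willingness to comply, judged at entry. Read as covering later conduct, they would turn every deviation into an eligibility breach, and the separate dosing clause in SAP 3.4 would have no purpose. This does not close the gap.

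**Steroid use will be visible anyway.** SAP 5.8 summarizes important deviations by category, and SAP 8.12 summarizes concomitant medications. That is true, and it lowers the stakes. It does not change who is in the per-protocol analysis.

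**Redaction.** SAP 3.5 is hidden and may define a further set that deals with this. That limit stands. The readable definition in 3.4 differs from Protocol 9.2.4 whatever 3.5 contains.

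**Stronger readings that a reader might infer**

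- *That the primary analysis is undermined or loses power.* It uses the full analysis set and, by formula [1] in SAP 6.1.2, all recorded diary days. Keeping observed days after rescue is a legitimate choice, and an excess of users on placebo would make it conservative. Nothing in SAP 3.4 bears on it.
- *That the tension between 4.3 and Appendix C decides which days count.* Section 4.3 allows withdrawal from study drug alone. A patient who stops drug but stays in the study complies with 4.3 and still contributes later days.
- *That Section 4.3 should be softened to match Appendix C.* That would loosen a safeguard.
- *That nerve blocks and devices should be banned during treatment.* Exclusion d ("The patient has used an intervention/device (eg, scheduled nerve blocks) for headache during the 4 weeks prior to screening") stops at screening. The documents show a choice not to restrict them as such later, not an error.
- *That the list of prohibited drugs cannot be found.* Section 7.10 says "Details of prohibited medications are found in Section 5.6", and 5.6 names none, but 5.6 itself points to Appendix H for preventives. This is editorial.

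**Conclusion.** The point holds for the per-protocol set. Protocol 9.2.4 and SAP 3.4 differ on important deviations, the SAP prevails, and the difference is not declared. A patient who takes systemic steroids after randomization, is kept on treatment by the sponsor (or takes them after the last dose) and completes the study remains in the per-protocol repeat of the primary and secondary analyses.

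The size is small for one patient, about 0.014 to 0.041 attacks per week in a group mean on the assumptions above. It becomes noticeable only if several more are kept in one group than in the other. The documents give neither the number of such patients nor the steroid effect. The conclusion assumes that the use would be judged an important deviation, which Appendix C makes possible but not automatic, and that the redacted SAP 3.5 holds no further rule.

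**What to change.** Add to the exclusions in SAP 3.4: *or any other important protocol deviation, including use of medications prohibited by Appendix H, as determined before unblinding*. This brings the SAP into line with Protocol 9.2.4, and the statement in SAP Section 16 then holds on this point.

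The cost is one clause in the SAP and a slightly smaller per-protocol set. No new data are needed, because Protocol 5.6 already requires start and stop dates for all concomitant medication. No new analysis is needed, because the per-protocol repeat is already planned. The primary analysis in the full analysis set does not change.
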